After patient participants enroll in the study, therapy schedules will be obtained from clinic staff to facilitate the scheduling of video recordings. Prior to recording a treatment session, a study team member will confirm with the OT that the session is appropriate for recording. Sessions are appropriate for recording if: 1) more than 50% of the session is anticipated to involve interventions targeting functional deficits related to UE motor impairment (e.g., activities of daily living involving use of the hands/arms, UE sensorimotor interventions, etc.); and 2) the session does not include a formal evaluation such as a progress report, evaluation, or discharge report (though intermittent assessment is allowed as this is standard practice). After confirming session appropriateness, study staff will be on-site to set up the video camera. Patient and OT participants will verbally confirm consent to be recorded prior to each recorded session. For each treatment session, every attempt will be made to place the video camera in a way that is both unobtrusive and able capture treatment activities without inadvertently capturing non-participants in the background. A study team member will be on-site during all video recordings, though

not necessarily in the treatment area, in an effort to decrease risk of participant behavior change (Asan & Montague, 2014).

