Video Recording Setup: Study team members will set up a stationary camera mounted to a tripod at a fixed point within the treatment area. This positioning will be carefully selected to face the patient and the OT without other patients/therapists in view to the best of our ability. In our previous study using comparable methods, the majority of sessions took place at a table near or against a wall without much movement around the clinic as therapy was focused on tabletop activities. If the therapist anticipates changing locations during the session they will make the study team member setting up the camera aware so they can monitor and adjust as needed. Additionally, we will adhere a bright neon sign to the video cameras stating that video recording is in progress, as well as verbally notify patients and therapists in the immediate vicinity that we will be recording, and they will have the option to verbally request that we choose an alternate spot for treatment/recording. In the event that other patients/therapist are recorded (e.g., walked into the background of the shot) we will blur faces/identifying features if the video is to be shared outside of our study team (e.g., during a conference presentation). Of note, in our small feasibility study using video observation methods, we had no trouble with this approach, and it was tolerated well by everyone in the clinical space. Video recording will start when the OT and patient participant are both in the treatment area and end at the conclusion of the last treatment activity. No more than 3 treatment sessions per patient participant and no more than 30 treatment sessions per OT practitioner will be recorded to increase the representativeness of our sample.

Data Collection

- **OT Demographics and Clinical Characteristics**

OT participants will be asked to provide demographic and clinical characteristics using a short questionnaire (refer to ‘OT Intake Questionnaire’ and ‘OT Demographics and Clinical Experience’ case report form). This data will be entered directly into REDCap by the participant using a secure survey link provided by a member of our study team upon enrollment.

- **Patient Demographics and Medical Information**

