categories: 1) Organ Functions, 2) Skills and Habits, or 3) Representations. All observed treatment activities will be categorized into one of the three RTSS categories, and their respective subcategories, or into a fourth category of assessment (not currently existing in the RTSS framework). All seconds of the session will be categorized as ‘active time’ (i.e., activities in each of the four categories), or ‘inactive time’ (i.e., when the patient does not engage in therapeutic activity for greater than 15 seconds consecutively). Treatment Targets: Treatment activities will also be coded with a corresponding treatment target, using a list of 75 potential targets developed through a review of three ICF Core Sets: 1) Rehabilitation Set, 2) Stroke Comprehensive, and 3) Neurological Post-Acute Comprehensive (Bickenbach et al., 2012). To help facilitate the categorization of treatment activities and targets, therapists will be asked to state the primary purpose for each treatment activity during video recording (e.g., “let’s work on stacking cones to increase your shoulder strength”), however clinical reasoning and chart reviews will also be employed to confirm coding accuracy. Active Ingredients: A coding scheme for measuring active ingredients was developed based on previously reported treatment ingredients (Cirstea & Levin, 2007; Gillen, 2015; Host et al., 2014; Stein, 2015; Taub & Uswatte, 2006; Wolf & Nilsen, 2015), discussion with OT practitioners in the field, and clinical experience. Active ingredients will be coded according to this schema as duration-based (time spent using the ingredient), frequency-based (number of occurrences), or both. Activities will be assessed for the following ingredients and coded accordingly: 1) whether feedback was provided, and in what way (e.g., knowledge of performance versus knowledge of results), 2) types of cues provided (e.g., verbal, tactile, etc.), 3) assistance provided by the therapist (e.g., active assisted range of motion) and 4) whether grading/shaping occurred, and in what way. All active ingredients will be coded as ‘present’ or ‘not present’ for each treatment activity. We will also code materials, equipment, and/or modalities used for each treatment activity (e.g., material ingredients). Once all active ingredients are coded with the INTERACT software, we will use the data to systematically describe the activities during treatment sessions using a template recommended by the authors of the RTSS (Tessa Hart et al., 2019). The total number of videos recorded per participant and per therapist will be tracked. This includes videos recorded during each study visit and any additional sessions deemed necessary by the study protocol. The average number of videos recorded per participant and therapist will be reported in the final study analysis to assess consistency in data collection. The number of videos successfully analyzed will be reported, alongside any discrepancies or challenges encountered during the analysis process (e.g., missing data, technical issues). These metrics will be included in the study report to provide transparency in the data collection and analysis process.

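### Every second is coded active or inactive, with no stated code or denominator rule for time when the patient is out of view

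*Combined protocol and SAP*

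**What the plan says.** Section III.D, Video Coding Analysis, sets the time rule: "All seconds of the session will be categorized as" either active time (activity in one of the three RTSS categories or assessment) or inactive time. Inactive time is defined by patient behaviour: "when the patient does not engage in therapeutic activity for greater than 15 seconds consecutively". The same section says that problems such as "missing data, technical issues" will be reported with the number of videos successfully analysed.

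Section III.C, Video Recording Setup, describes the view: "Study team members will set up a stationary camera mounted to a tripod at a fixed point within the treatment area". The position is also chosen to keep other patients and therapists out of shot. Movement is handled by warning: "If the therapist anticipates changing locations during the session", the therapist is to "make the study team member setting up the camera aware so they can monitor and adjust as needed". The section adds that in the earlier comparable study "the majority of sessions took place at a table near or against a wall without much movement around the clinic".

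Under Video Recording Procedures, a team member is on site for every recording, but "not necessarily in the treatment area, in an effort to decrease risk of participant behavior change".

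The Video and Photo Data paragraph names active time versus rest or setup, and upper-extremity repetitions, as quantities to be analysed.

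**The concern.** The two codes are meant to cover the whole session, yet inactive time can be judged only when the patient can be seen. If the patient moves without notice, or the view is blocked, the coder must still choose a code. A short gap may be carried along in the surrounding active code. A longer one may be taken as inactivity, or filled in from sound or context. The text does not say which, so two coders could reasonably differ, or could agree on the same unsupported code.

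At stake are the descriptive durations: active versus inactive time, time per RTSS category, and ingredients measured by time spent. These feed the account of standard care, and the method is to be published as a toolkit for other researchers, who would take over the same gap.

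**Working it through.** The plan gives no expected active share, session length or unseen share, so there is no figure of its own to reproduce. Simple bounds show the size.

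**Inputs**
- Two exhaustive codes and the 15-second definition of inactivity: Section III.D, Video Coding Analysis.
- Unseen share of the session, u: not in the documents; assumed 2% to 20%.
- True active share, a: not in the documents; assumed 70%, with 50% and 90% as checks. It is taken to be the same in seen and unseen time.

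**Formulas**
- All unseen time coded inactive: reported share = a(1 − u), an error of −a·u.
- All unseen time coded active: reported share = a(1 − u) + u, an error of +(1 − a)·u.
- Width of the range = u, whatever the value of a.
- Repetition total: low by about u if repetitions are spread evenly over the session.

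**Results for a = 70%**

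| Unseen share u | All coded inactive | All coded active | Repetition total low by about |
|---|---|---|---|
| 2% | 0.70 × 0.98 = 68.6% | 68.6 + 2 = 70.6% | 2% |
| 5% | 0.70 × 0.95 = 66.5% | 66.5 + 5 = 71.5% | 5% |
| 10% | 0.70 × 0.90 = 63.0% | 63.0 + 10 = 73.0% | 10% |
| 20% | 0.70 × 0.80 = 56.0% | 56.0 + 20 = 76.0% | 20% |

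At u = 10%, the range is 45.0% to 55.0% for a = 50%, and 81.0% to 91.0% for a = 90%.

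**With observable time as the denominator**
- The active share becomes a(1 − u)/(1 − u) = a, for any u, provided unseen time resembles seen time.
- If it does not, let b be the active share within unseen time. The truth is then a(1 − u) + b·u, with a now the active share in seen time. Because b lies between 0 and 1, the truth still falls inside the bounds above. That is why the bounds should be reported as well.
- Repetitions per observable minute are unaffected under the same proviso. The raw total stays low by about u.

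**Do other provisions in the plan correct the durations?**
- Reporting missing data and technical issues goes with the count of analysed videos. It sets no rule for unseen seconds inside a video.
- Treatment notes are compared with the video findings, including active treatment time (Patient Demographics and Medical Information), but not as a stated correction.
- Interrater checks cover at least 20% of videos, that is 30 of the planned 90 + 60 = 150. Both raters watch the same footage, so agreement does not show that an unseen stretch was coded correctly.
- Sub-categories may be added as analysis proceeds, but the example given is education, a kind of activity and not a state of visibility.

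**The case against.** The best answer is that little time may be lost. The earlier study was mostly at a table, every attempt is to be made to place the camera well, announced moves lead to adjustment, and someone is on site throughout. Nor are coders confined to the picture: therapists state the purpose of each activity aloud, and clinical reasoning and chart review support the coding. A gap of 15 seconds or less does not by itself meet the definition of inactivity. Active versus inactive time is not among the listed primary outcomes (activity types, targets and active ingredients), and no hypothesis test depends on it. Figure 3 is not shown and the coding manuals are not among the documents, so either may already hold a code for unseen time.

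Much of this stands and limits the size of the point. It does not remove it. The mitigations cover anticipated moves and typical sessions; an unannounced move or a blocked view can go uncorrected while staff are elsewhere. If the manual does have such a code, the protocol's rule that every second is active or inactive contradicts it and needs reconciling.

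Three stronger readings are tempting, and the documents support none of them:
- **The camera will lose the patient and the figures are wrong.** No unseen share is given, and it may be close to zero.
- **Functional, mobile work is understated relative to tabletop work.** Nothing says that such sessions leave the frame more often, planned moves are the ones that prompt camera adjustment, and coding unseen time as active would push the share up.
- **The two-code rule causes low repetition counts.** Lost view lowers those counts under any time code.

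**Conclusion.** The point holds as a gap in a stated rule. As written, any stretch in which the patient cannot be seen must be coded active or inactive without a basis for either, and nothing else in the visible text corrects the resulting durations. The active share could be off in either direction, within a range equal in width to the unseen share. With 70% truly active, 10% unseen gives an error between −0.70 × 10 = −7 and +0.30 × 10 = +3 percentage points; 2% unseen gives −1.4 to +0.6. Repetition totals would be low by about the unseen share, through lost view alone.

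These sizes rest on assumed values, and on unseen time resembling seen time and repetitions being evenly spread. The actual unseen share is unknown. A change is justified because it is cheap and would measure that share, not because a large bias has been shown.

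**What to change.** Before coding starts:

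1. Add a third, mutually exclusive code, 'not observable' (out of frame, blocked, equipment failure), to Video Coding Analysis and to the INTERACT scheme. If the coding manual already has one, reconcile the protocol text with it.
2. Use observable time as the denominator for all time shares.
3. Report repetitions and ingredient counts per observable minute, alongside the raw totals.
4. Report the not-observable share separately for the stroke and SCI cohorts.
5. Bound the main time shares by counting not-observable time as all active and then as all inactive.

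The cost is one more code for raters to learn and slightly less analysable time per session. No extra participants or recordings are needed. A code added after coding has begun would mean going back over videos already coded.

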The work outlined in this proposal is innovative in several ways. First, our group will be the first to incorporate the RTSS to characterize standard care in stroke or SCI occupational therapy. This approach will inform not only stroke research but will also elucidate ways OT researchers can use the RTSS in their own work to better describe experimental and control interventions. Additionally, this work will utilize a video-based observational study design to comprehensively analyze and describe intervention details that simply could not be characterized using other observational methods (e.g., non-video observation, chart reviews). There is a growing body of evidence supporting the use of video-based observation over traditional approaches to capture details that otherwise get missed (Golembiewski et al., 2023). As an example, previous work by Lang and colleagues (2009) published a ground-breaking paper on the number of repetitions stroke patients completed, on average, per treatment session. While the results of that work were incredibly important to the field, the methodology limited the authors to only counting repetitions without characterizing other intervention factors that may have had an influence on neurorecovery (Kleim & Jones, 2008). Non-video observation limits the ability to measure interrater reliability, re-watch the intervention to ensure nothing was missed, and capture other ‘ingredients’ of the intervention (e.g., the types of verbal cues provided, modalities used, patient level of engagement, etc.) that may play a critical role in intervention efficacy. Our approach will allow us to comprehensively describe all aspects of the intervention, a critical need identified in the field. This innovative research will help researchers 1) identify knowledge gaps and plan future directions in stroke rehabilitation research, 2) provide a rationale for control interventions that are comparable to true ‘standard care’ in stroke rehabilitation trials, and 3) develop an empirically based approach to video observation using the RTSS and disseminate these findings as a ‘toolkit’ for OT researchers to use across diagnoses and settings.

C. Approach

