All treatment sessions will be video recorded and coded electronically using Mangold INTERACT video analysis software to allow us to analyze both duration (e.g., time spent on active therapy versus rest/setup) and frequency (e.g., number of UE repetitions) data, as well as control for significant participant behavior change (Asan & Montague, 2014). An overview of the video coding framework is presented in **Figure 3**. We will make every attempt to categorize all treatment activities into these categories, though we may find during our analyses that a sub-category needs to be added (e.g., education) and it may be updated through an iterative process. The primary outcomes for this study are the identification of 1) the types of treatment activities (e.g., ‘Organ Function’ versus ‘Skills and Habits’ activities), 2) the targets most often addressed (e.g., increasing strength, improving ability to grasp/release objects, increased independence with dressing, etc.), and 3) the active ingredients of interventions used to treat adult stroke patients with UE hemiparesis.

- Feasibility and Acceptability Surveys

After data collection is complete, we will administer electronic surveys via REDCap to all OT practitioner and patient participants who had at least one OT session recorded to gauge their acceptability and comfort with being video recorded. In addition to study-specific questions about logistics, scheduling, and overall approach,

we will also incorporate well-established implementation science survey metrics to quantify acceptability of this approach (Weiner et al., 2017). Refer to 'OT Practitioner Feasibility Survey' and 'Patient Participant Feasibility Survey' documents for the questions we will ask. Of note, consent to complete this survey will be provided in the paper consent form at the beginning of the study for both video recordings and the survey at the end of their data collection.

Data Management

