
Video Coder Training

Each video analysis will be conducted by trained video raters in several passes to determine 1) treatment categories and targets, 2) durations, frequencies, and repetitions, and 3) active ingredients. A minimum of 20% of all the videos will be assessed for interrater reliability ($\geq 90\%$), and minor adjustments to the coding manual may be made. To ensure fidelity, all raters will participate in comprehensive training with a member of our study team and will

be provided with instruction manuals developed for this analysis. Consistent with previous studies, raters will be required to code a mock treatment session using the established framework and reach 90% agreement with the coinvestigator prior to independently coding video data (Lang et al., 2009; Winstein et al., 2003). Videos will be coded and analyzed largely by occupational therapy doctorate (OTD) students in their second or third year of the program, which we previously demonstrated worked well with high interrater reliability (97%) for RTSS treatment groups (Wengerd, 2019).

Statistical Analysis

Data coded using INTERACT will be entered into REDCap and subsequently analyzed using SPSS Statistics. Descriptive statistics will be used to describe the study sample, and all observed treatment categories, treatment sub-categories, treatment targets, and active and material ingredients. Shapiro-Wilk tests will be conducted to assess for normality. Survey results will be reported using descriptive statistics and will be used to inform our video-based observation toolkit development in order to maximize implementation and acceptability of this approach.

Development of a Video Observation Toolkit

The overarching purpose of this Aim 2 is to manualize an approach for video observation to characterize rehabilitation interventions comprehensively using the RTSS framework. This manual will cover the following areas to advance the fields of rehabilitation and implementation science: 1) a comprehensive overview of the pros and cons of video observation compared to traditional implementation science approaches (e.g., chart review, surveys), 2) a step-by-step guide on how to create buy-in with community stakeholders to conduct this kind of work, and how to setup video observation that is unobtrusive to standard care; and 3) a detailed description of how to comprehensively analyzes video observations using the RTSS framework in OT practice settings.

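### Does asking therapists to state each activity's purpose on camera undermine the description of standard care?

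*Combined protocol and SAP*

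**What the plan says.** Section III.D, Video Coding Analysis, says that "therapists will be asked to state the primary purpose for each treatment activity during video recording". The reason given is to make categories and targets easier to assign, and the example is a sentence spoken to the patient. The same section adds clinical reasoning and chart review as checks on coding. Section III.C, Patient Demographics and Medical Information, also has treatment notes of observed sessions reviewed to confirm targets.

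Three other places bear on the point:

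- III.C, Video Recording Procedures: "A study team member will be on-site during all video recordings", though possibly outside the treatment area, "in an effort to decrease risk of participant behavior change".
- III.D, Video Coder Training: raters code each video "in several passes to determine 1) treatment categories and targets, 2) durations, frequencies, and repetitions, and 3) active ingredients".
- III.D, Development of a Video Observation Toolkit: the manual will teach "how to setup video observation that is unobtrusive to standard care".

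Section II.B, Innovation, makes the broad claim: "Our approach will allow us to comprehensively describe all aspects of the intervention".

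**The concern.** The study sets out to describe what therapists ordinarily do, and it takes steps to limit behavior change. Asking therapists to announce a purpose for every activity alters the therapist-patient talk that is being recorded. Verbal cues are a coded ingredient, and each ingredient is scored present or absent per activity, so one prompted sentence could in principle set a code. Section III.C, Video and Photo Data, also leaves room for a sub-category such as education to be added during coding.

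If prompted speech were counted, standard care would look more explanatory than it is. Later trials could then build control arms on that picture, and the toolkit could pass the instruction on. Once the sessions are recorded, the unprompted behavior cannot be recovered. Staff are on site anyway and recording is to "end at the conclusion of the last treatment activity", so an off-camera debrief looks like an easy substitute.

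**Working it through.** The plan gives no figure to reproduce, and the analysis is descriptive. The check has five steps.

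**1. What is lost.** Let q be the unprompted rate of purpose statements per activity, and c the chance that the request produces one where none would have been made. Assume spontaneous statements still occur. The observed rate is

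r = q + (1 − q)c, so q = (r − c)/(1 − c) for c from 0 to r.

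At an illustrative r = 0.80:

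| c | q |
|---|---|
| 0 | 0.80 |
| 0.5 | 0.30/0.50 = 0.60 |
| 0.6 | 0.20/0.40 = 0.50 |
| 0.8 | 0/0.20 = 0 |

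At c = 1, r = 1 whatever q is. Section III.B plans 90 + 60 = 150 sessions, all under the request, so no unprompted comparison exists. The unprompted rate is not identifiable.

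**2. Whether the plan reports it.** The primary outcomes in III.C, Video and Photo Data, are activity types, targets and active ingredients. The ingredients listed in III.D are feedback, cues, therapist assistance and grading or shaping, plus materials, equipment and modalities. Purpose statements appear in neither list. An education sub-category is only a possibility, and it is raised for classifying treatment activities. Nothing says that a one-sentence introduction to some other activity would be placed there.

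**3. Effect on durations.** The documents give neither activities per session nor statement length. Assume 5 to 10 activities, 5 to 10 seconds per statement and sessions of 30 to 60 minutes. Prompted speech is then 5 × 5 = 25 seconds to 10 × 10 = 100 seconds, which is 25/3,600 = 0.7% to 100/1,800 = 5.6% of session time. Even if all of it were added time, the effect on durations would probably be small.

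**4. Effect on the cue code.** This is the only route into a planned result. In the worst case every prompted sentence is scored as a verbal cue, and at full compliance the cue code would be present in 100% of activities. The supplied text does not say that raters will do this. Purposes serve the category and target pass, while ingredients are coded in a separate pass by raters trained to a manual. The manual was not supplied and Figure 3 is not shown. The rule is also applied at coding, so it can be set or tightened after recording without losing any planned code.

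**5. What the debrief would cost.** At an assumed 1 to 3 minutes per session, 150 sessions need 150 to 450 minutes, or 2.5 to 7.5 staff hours. A therapist at the 30-session cap would give 30 to 90 minutes. Rater time to match lists to activities is extra. The larger cost is in measurement. Categories follow from an activity's primary target, and targets come from a list of 75. A spoken statement sits at its activity on the video. A debrief gives a recalled list, matched by order and possibly taken by someone who did not watch the session.

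**The case for a change.** The strongest case for a change is that the protocol names behavior change as a risk, claims to describe the whole intervention and then adds a scripted element to every session, without listing it as a limitation. Notes and chart review already inform targets, so the request is not the only source. A sentence in the protocol telling raters to tag the statements and keep them out of the cue and education codes would cost almost nothing.

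Part of this stands. The request does put study-prompted speech into every session, and the unprompted rate cannot be recovered. A report or toolkit describing these sessions would do well to say that the statements were requested.

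The rest does not carry. The passages are in tension but do not contradict each other: one concerns where staff stand, another how observation is set up, and neither promises that therapists receive no instruction. The sessions already carry a visibly signed camera and a verbal consent check, so the design does not claim to leave no trace. Notes are retrospective, and the contemporaneous statement may supply what they lack. The tagging sentence would write down a coding rule that the manual may already contain and that trained raters would probably apply anyway. No planned result is shown to be wrong without it.

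**Conclusion.** No change to the plan follows. The demonstrated loss is confined to one quantity, the unprompted rate of purpose statements, which the plan does not set out to report. No size of bias in the planned results can be derived from the documents, and it may be zero. Moving the question off camera would give up precision in the first two primary outcomes, activity types and targets, to protect that unreported quantity. Keeping the spoken statement is therefore a defensible trade-off.

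This rests on two assumptions: that raters do not score a requested purpose statement as a verbal cue, which the supplied text neither confirms nor denies, and that no unprompted rate of explanation is later reported from these recordings. If an education sub-category were added and one-sentence introductions were counted in it, that result would have to be described as prompted.
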